1 BACKGROUND AND RATIONALE

1.1 Introduction

This is a randomized, controlled trial evaluating the effect of “optimal PEEP” compared to standardized PEEP titration on duration of mechanical ventilation in obese adult patients with acute respiratory failure requiring mechanical ventilation.

1.2 Description of Intervention

All patients in both groups will have an esophageal balloon catheter inserted by a research investigator. The catheter will be inserted into their nare while upright (head of bed >30 degrees) to a depth slightly more than the estimated distance from the lower sternum to the back of the ear (typically around 60 cm). Gastric positioning will be confirmed with abdominal compression testing and the catheter then retracted 10 – 20cm into the lower esophagus. Placement will be confirmed with the presence of cardiac oscillations on the esophageal probe. The probe will then be secured to the patient’s nasal opening using tape. Pressures (Pes, Paw, and Ptp) are measured directly through the ventilator. Values of Paw, Pes, and Ptp will be collected daily in both groups. The waveforms of Paw, Pes, and Ptp will be visualized on the ventilator. Ptp is obtained from Paw – Pes. PEEP will be increased on the ventilator to achieve a Ptp between 0 and +2 cm H₂O (“Optimal PEEP”). Measurements will be obtained daily and adjustments to PEEP will occur daily. PEEP will be reduced below Optimal PEEP in the setting of hemodynamic compromise (requiring increasing vasoactive medications for blood pressure support).

1.3 Relevant Literature and Data

The use of PEEP in mechanical ventilation is important to reduce the collapse of alveoli between breaths. This atelectasis increases the patient’s work of breathing and impairs oxygenation. In addition, atelectrauma can lead to ventilator-induced lung injury (VILI) through repetitive shear injury. (1) There is a patient-specific response to PEEP titration, but PEEP titration is frequently not guided by individual patient data. Obese patients have less compliant chest walls, which increases the apparent airway pressure required to provide mechanical ventilation. Titration of PEEP to levels high enough to prevent atelectasis and improve chest wall compliance in these patients yields apparently unsafe pressures. Yet these pressures are not likely transmitted to the alveoli. (2) In order to evaluate the pressure transmitted to the alveoli, one should consider the pleural pressure. Direct measurement of the pleural pressure is highly invasive and poses risk to the patient. However, estimation of the pleural pressure using an esophageal pressure monitor is significantly less invasive and provides an acceptable alternative for estimation of transpulmonary pressure (Ptp). (3–6) Preliminary work by members of the research group evaluated time to wean from mechanical ventilation in obese patients requiring tracheostomy. Use of Ptp to guide PEEP choice resulted in a significant reduction in the median time to wean, from 14 days to 3.5 days (p=0.012). (7) We propose that esophageal pressure measurement can guide optimal PEEP selection in obese patients who require mechanical ventilation and reduce their time on the ventilator.

2 STUDY OBJECTIVE

The overall purpose of the study is to evaluate the effect of using an esophageal balloon determined optimal PEEP management strategy on the duration of mechanical ventilation in obese adult patients with acute respiratory failure requiring mechanical ventilation.

2.1 Primary Objective

To determine if titration of PEEP to Optimal PEEP results in a reduction of the duration of mechanical ventilation in obese adults in a medical ICU.

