Study Design	Randomized-controlled clinical trial. Patients will be enrolled within 4 days of mechanical ventilation and randomized 1:1 to titration of PEEP based on esophageal balloon pressures or based on the "High PEEP" ARDSnet PEEP/FiO ₂ table. All patients will have esophageal balloons placed with baseline measurement of Ptp. Patients randomized to the intervention arm will then undergo titration of PEEP based on Ptp measurements to achieve "Optimal PEEP," defined as end expiratory Ptp of 0 to +2 cm H ₂ O.

Subject Population key criteria for Inclusion and Exclusion:	
Inclusion Criteria: Obese adults (BMI ≥ 40) admitted to the medical ICU at UNC Hospitals or Vidant Medical Center at ECU with acute respiratory failure requiring mechanical ventilation.
 
Exclusion Criteria:
 
 1. Refusal to give consent by subject or LAR 2. Abdominal compartment syndrome 3. Chest tube for pneumothorax 4. Having been on a ventilator for >4 days 5. Suspicion of or known intracranial hypertension 6. Anticipated extubation within 24 hours 7. Chronic ventilator dependence 8. Condition that precludes placement of an esophageal balloon (esophageal or nasopharyngeal pathology preventing insertion of the esophageal balloon catheter, severe thrombocytopenia, or coagulopathy) 9. Incarceration 10. Not expected to survive >48 hours 11. Unable to obtain consent from subject or LAR 12. Unable to obtain consent due to a language barrier
Number Of Subjects	76 patients
Study Duration	Each subject's participation will last for up to 28 days. The entire study is expected to last about 12-24 months.
Study Phases	
(1) Screening: Screening for eligibility and obtaining consent for enrollment.
 
(2) Pre-Intervention: Esophageal balloon placed and baseline data collected.
 
(3) Intervention: PEEP titrated to achieve Optimal PEEP in the intervention group. Ptp Measurements will be obtained daily and adjustments to PEEP will occur daily.
 
(4) Subject Completion/Withdrawal: Study will conclude for each patient at 28 days after enrollment or hospital discharge.

Efficacy Evaluations	Primary evaluation measurements that will be used to assess the efficacy of the intervention are ventilator free days at day 28. Differences between control and intervention groups will be attributed to differences in PEEP management.

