3 INVESTIGATIONAL PLAN

3.1 Study Design

We will conduct an open label randomized controlled clinical trial to evaluate the impact of titration to Optimal PEEP compared to use of a standardized PEEP table on the duration of mechanical ventilation in obese patients with acute respiratory failure. Patients will be followed for 28 days to evaluate for ventilator-free days. Blinding of the clinical team will not be possible due to the differences in treatment approach, including the performance of spontaneous breathing trials.

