4.2 Randomization, Concealment, and Blinding

Patients will be randomized 1:1 in random blocks of 2, 4, or 6 to optimal PEEP vs standard PEEP management. Allocation concealment will be performed through the REDCap randomization module. Due to the obvious treatment differences between the two groups, blinding of treatment group will be impossible. However, we will have one outcome assessor who will have access only to the data necessary to determine the primary outcome (VFD at 28-days), and this assessor will be blinded to treatment group using built-in REDCap tools.

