5 STUDY EVALUATIONS AND MEASUREMENTS

5.1 Measurements

Procedures for PEEP and FiO2 Titration

Both groups will have their FiO2 titrated based on results of the PaO2 from an arterial blood gas, if available, or SpO2 values if no arterial blood gas is obtained. PEEP titration will vary by group as below.

Setting PEEP in Intervention Group

The waveforms of Paw, Pes, and Ptp will be visualized on the ventilator. Ptp is obtained from Paw – Pes. PEEP will be increased on the ventilator to achieve a Ptp between 0 and +2 cm H₂O (Optimal PEEP). Measurements will be obtained daily and adjustments to PEEP will occur daily. PEEP will be reduced below Optimal PEEP in the setting of hemodynamic compromise (requiring increasing vasoactive medications for blood pressure support).

Setting PEEP in Control Group

PEEP in the control group will be determined by High PEEP ARDSnet PEEP/FiO₂ table. Titration of PEEP will occur when clinically indicated by PaO₂ or SpO₂, and FiO₂. We chose the High PEEP table based on the clinical suspicion that obese patients may require higher PEEP levels on average than non-obese patients to balance the additional pressure of their chest wall. In addition, EPVent2, a study of esophageal balloon PEEP titration in patients with ARDS utilized the High PEEP table. Patients with moderate and severe ARDS benefit from higher levels of PEEP. (8)

Procedures for Assessment of Readiness for Extubation

Both groups will have a daily assessment of readiness for extubation performed by the Respiratory Therapist and bedside RN according to the standard clinical protocol. Criteria for both groups to undergo a spontaneous breathing trial (SBT) will be the following:

- 1) Not in prone position
- 2) No increased ICP
- 3) No active seizures
- 4) No alcohol withdrawal requiring escalating treatment
- 5) No active myocardial ischemia in discussion with nursing or physician
- 6) No unstable spine fractures
- 7) No free muscle flaps
- 8) FiO₂ ≤ 50% and SpO₂ ≥ 90%
- 9) Minute Ventilation < 15 L/min
- 10) Minimal vasopressors (norepinephrine < 5mcg/min or 0.05 mcg/kg/min, dopamine/dobutamine ≤ 5 mcg/kg/min)
- 11) HR < 140
- 12) RR ≤ 35
- 13) SBP > 90 and < 180

Failure of an SBT will be demonstrated if any of the following criteria are met:

- 1) SpO₂ < 90% sustained ≥ 5 minutes
- 2) Spontaneous VT ≤ 4ml/kg IBW – sustained ≥ 5 minutes
- 3) Respiratory Rate ≥ 35/min
- 4) Rapid Shallow Breathing Index >105

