- 5) Other signs of respiratory distress (distress = 2 or more)
- 6) HR > 140
- 7) Marked accessory muscle use
- 8) Abdominal paradox (belly breathing)
- 9) Diaphoresis

Failure of an SBT will be determined by the bedside RT based on current policy (PolicyStat ID: 4745433). If a patient fails an SBT, they will be returned to their previous ventilator settings until the next daily assessment. If the patient tolerates a 30-minute SBT, they will be returned to their previous ventilator settings for 60 minutes, then extubated to an appropriate oxygen delivery device. Ventilator settings during the SBT and extubation procedures will vary between groups as below. Blinding of the respiratory therapist determining eligibility for SBT to treatment arm will not be possible because of the differences between SBT protocols. However, the study team will make no determinations of readiness for extubation. If a member of the study team is on service during the time of potential enrollment, these patients will be excluded to avoid bias.

SBT and Extubation Procedure for Intervention Group

Patients in the Intervention group will undergo an SBT regardless of their PEEP level. The PEEP that generates a Ptp of 0 will be considered their optimal PEEP, and this will not be lowered for the SBT. The Intervention Group SBT will consist of a trial of a pressure support of 5 cm H₂O and Optimal PEEP.

SBT and Extubation Procedure for Control Group

Patients in the Control group will undergo an SBT **when they reach a PEEP \leq 8 cm H₂O**. This is the current standard of care based on the SBT protocol at UNC Hospitals. SBT and extubation prior to meeting these criteria will be based on primary medical team's discretion and will be recorded for analysis and safety tracking.

Procedures for ventilator weaning after tracheostomy

Any patient who fails to be eligible for extubation or fails extubation will be eligible for tracheostomy per usual unit protocol. The study team will play no part in the decision to proceed with tracheostomy for ventilator weaning. After tracheostomy, it is routine practice to forego SBT and proceed with trials of liberation from the ventilator with oxygen delivered by an aerosol tracheostomy collar ("trach collar trials" or TCT). The same criteria are used to perform a TCT as an SBT above. The two groups will have different approaches to TCT.

TCT Procedure common to both groups

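### The primary objective credits PEEP titration, but the arms also differ in breathing-trial rules and speaking-valve use, so a result can be credited only to the whole strategy

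*Combined protocol and SAP*

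**What the plan says.** Several places describe what the trial tests, with different breadth.

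- Section 2.1: "To determine if titration of PEEP to Optimal PEEP results in a reduction of the duration of mechanical ventilation". The first sentence of Section 3.1 draws the same contrast, titration against a PEEP table.
- Section 1.1 uses similar shorthand for the comparator: "compared to standardized PEEP titration on duration of mechanical ventilation in obese adult patients".
- Synopsis, Efficacy Evaluations: "Differences between control and intervention groups will be attributed to differences in PEEP management".
- Section 2 is broader: "optimal PEEP management strategy on the duration of mechanical ventilation". Section 4.2 labels the randomised arms in similar terms: "to optimal PEEP vs standard PEEP management".

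Section 5.1 then sets the weaning procedures. A common list opens with "Criteria for both groups to undergo a spontaneous breathing trial (SBT) will be the following" and includes FiO₂ of 50% or less. It is followed by arm-specific rules: "Ventilator settings during the SBT and extubation procedures will vary between groups as below". Intervention patients have an SBT at any PEEP, on pressure support 5 cm H₂O with Optimal PEEP kept. Control patients have one once PEEP is 8 cm H₂O or less, described as the standard of care at one of the two hospitals; earlier SBT or extubation is left to the primary team. After tracheostomy, intervention patients have collar trials only with a speaking valve, while control patients may use one but need not.

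Section 3.1 mentions "differences in treatment approach, including the performance of spontaneous breathing trials", but as the reason blinding is impossible and not as a limit on interpretation.

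**The concern.** The primary outcome is ventilator-free days to day 28. It depends on when a patient is allowed an SBT, at what settings, and how collar trials are run. All of these differ between arms by protocol, in addition to how PEEP is chosen.

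A positive result read as Section 2.1 is worded would credit balloon-guided titration with any effect of those other rules. That matters to a unit deciding what to adopt. Lifting a PEEP ceiling for SBTs, or requiring a speaking valve, needs no esophageal balloon. Running the SBT at the PEEP that gives a transpulmonary pressure (Ptp) of 0 does need one. No analysis in Section 6.2 separates these parts, and the design could not separate them.

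**Working it through.** This is a question of attribution, so the plan has no figure of its own to reproduce on it. The sample size in Section 6.3 does not depend on the cause of a difference and is not in dispute. The check compares the arms and then counts columns in the printed PEEP tables.

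**1. The arms side by side (Section 5.1)**

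| Component | Intervention | Control | Is it titration? | Is it PEEP management, read broadly? |
|---|---|---|---|---|
| Choice of PEEP | Ptp 0 to +2 cm H₂O | High PEEP table | Yes | Yes |
| PEEP limit for SBT entry | None | ≤ 8 by default; earlier at primary team's discretion | No | Yes |
| SBT settings | Pressure support 5, Optimal PEEP kept | Not given, except that settings differ by arm | No | Yes, for the PEEP part |
| Speaking valve in collar trials | Required | Optional | No | No: used off the ventilator |

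Section 5.1 gives the valve a rationale linked to Optimal PEEP, but a rationale does not make it a PEEP setting.

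**2. How strict the control ceiling is (Appendix 12.1)**

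Higher PEEP table, FiO₂/PEEP in order: 0.3/5, 0.3/8, 0.3/10, 0.3/12, 0.3/14, 0.4/14, 0.4/16, 0.5/16, 0.5/18, 0.5–0.8/20, 0.8/22, 0.9/22, 1.0/22, 1.0/24.

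- Columns compatible with FiO₂ ≤ 0.5: the first 10, counting 0.5–0.8 because it includes 0.5.
- At FiO₂ 0.3: 2 of 5 columns have PEEP ≤ 8, so 3 exceed it.
- At FiO₂ 0.4–0.5: 0 of 5 columns have PEEP ≤ 8. PEEP is 14, 16, 16, 18, 20, which exceeds 8 by 6, 8, 8, 10 and 12 cm H₂O. The distance down to 0.3/8 is 4, 5, 6, 7 and 8 table steps.
- Above the ceiling in total: 3 + 5 = 8 of 10. Leaving out the 0.5–0.8 column gives 3 + 4 = 7 of 9.

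A control patient kept on the table at FiO₂ 0.4–0.5 therefore meets the shared FiO₂ criterion but is not due an SBT by default. An intervention patient at the same FiO₂ who meets the other shared criteria is.

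**3. Where the gap comes from**

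Lower PEEP table, same appendix: 0.3/5, 0.4/5, 0.4/8, 0.5/8, 0.5/10, 0.6/10, 0.7/10, 0.7/12. At FiO₂ 0.4–0.5, 3 of 4 columns have PEEP ≤ 8. The gap comes from pairing the High PEEP table with a ceiling of 8, and not from the ceiling alone.

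**4. What cannot be computed**

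Column counts are not patients or hours. The documents give no time spent at each setting, no SBT delay, no rate of early control SBTs, no tracheostomy rate and no standard deviation for ventilator-free days. The effect of the weaning rules or the valve cannot be sized.

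**The case against.** The strongest reply is that this is only wording. Section 2, the parent of 2.1, already speaks of a management strategy. The title compares with usual care. Every arm-specific rule is written out openly, and the randomised comparison is sound. All of that stands. It does not rescue Section 2.1 or the first sentence of Section 3.1, which name titration, or the Synopsis sentence, which states in advance how a difference will be credited.

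The second reply is that dropping the ceiling follows from the titration. If Optimal PEEP is above 8 and is not to be lowered for the SBT, a ceiling of 8 would block the SBT or force PEEP off target. This also stands. A reader might infer that the SBT rule is an add-on unrelated to titration; the documents do not support that. The two are linked. Even so, an entry rule for an SBT is a different act from setting PEEP, and the control arm carries a strict version of it.

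Third, the non-PEEP part is limited. The valve concerns only tracheostomy patients, and control patients may use one too. Early SBT at the team's discretion softens the ceiling by an unknown amount. Control SBT settings are not given, so a reader should not infer that pressure support differs between arms. These points limit how much can be said about size. They do not restore attribution to titration.

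**Conclusion.** The point holds as one of attribution. The trial can support a conclusion about the strategy as delivered: Ptp-guided PEEP, SBT at Optimal PEEP without a ceiling, and collar trials with a required valve, against the table-based usual-care strategy. It cannot support a conclusion about titration alone. The SBT PEEP rules can be read as PEEP management; the speaking valve cannot.

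The only size the documents give is structural: 8 of 10 eligible-FiO₂ columns in the control table lie above the SBT ceiling, including all 5 at FiO₂ 0.4–0.5. This assumes that control patients are kept on the table and that the primary team does not act early.

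Two stronger readings are tempting. One is that the comparison is confounded or invalid. It is not: the weaning rules are part of the assigned treatment, and randomisation protects the comparison of strategies. The other is that the weaning rules would explain most of any benefit. Nothing in the documents bears on that. Power figures for an assumed shift would show only that the t-test cannot tell one cause from another, and would rest on a standard deviation of ventilation duration (2.9 days), not of ventilator-free days.

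**What to change.** Reword Objective 2.1 along these lines: *To determine whether a strategy of Ptp-guided PEEP, SBTs at Optimal PEEP without a PEEP ceiling, and trach-collar trials with a required speaking valve shortens mechanical ventilation relative to the table-based usual-care strategy, in obese adults in a medical ICU.*

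Replace the Synopsis sentence under Efficacy Evaluations with: *Any difference between arms is credited to the strategy as a whole and not to any single component.*

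Align the other places that carry the narrower wording: the Synopsis objective and hypothesis, Sections 1.1 and 2, the first sentence of Section 3.1, and Section 6.2. Changing 2.1 alone would leave the protocol inconsistent.

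Optionally, report by arm, as description only:

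- time to first SBT, with the PEEP and FiO₂ at that time;
- early control SBTs, which Section 5.1 says are recorded but for which Section 5.2 has a line only for early extubation;
- speaking-valve use among tracheostomy patients.

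These items show what was delivered and should not be used to split the effect.

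The cost is wording changes in eight places and a narrower headline claim. The optional items need light chart abstraction and a line in Section 5.2. No SBT, PEEP or valve rule changes, and neither does the sample size or the primary test.

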3 INVESTIGATIONAL PLAN

3.1 Study Design

We will conduct an open label randomized controlled clinical trial to evaluate the impact of titration to Optimal PEEP compared to use of a standardized PEEP table on the duration of mechanical ventilation in obese patients with acute respiratory failure. Patients will be followed for 28 days to evaluate for ventilator-free days. Blinding of the clinical team will not be possible due to the differences in treatment approach, including the performance of spontaneous breathing trials.

3.2 Allocation to Treatment Groups

Patients will be randomized 1:1 in blocks of 2, 4, or 6 to Optimal PEEP vs High-PEEP ARDSnet PEEP/FiO₂ table PEEP management. Randomization will be completed using the REDCap randomization module.

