Safety Evaluations	Periodic review will be performed by the NC TraCS DSMB. They will review aggregate safety data after 25, 50, and 75% enrollment to ensure there are not safety differences between the groups in hypotension requiring vasopressors and development of pneumothorax. All patients will have

continuous monitoring of HR, BP, and oxygenation per ICU protocol to monitor patient safety.

Statistical And Analytic Plan

This is a randomized, controlled trial to evaluate the effect of using Optimal PEEP based on an esophageal balloon measurement on duration of mechanical ventilation. We hypothesize that using Ptp to identify optimal PEEP will reduce time on the ventilator and therefore increase the ventilator free days at day 28. The primary outcome is the number of ventilator-free days, defined as the number of days alive and ventilator-free by day 28. Differences between the two groups in the primary outcome will be analyzed using independent t-tests and a linear regression model adjusting for BMI, abdominal girth, and Ptp.

DATA AND SAFETY MONITORING PLAN

The PI will be responsible for maintaining patient data and ensuring accuracy of the data collected. All patient data will be collected using REDCap through the NC TraCS system. REDCap allows for immediate data validation and range setting to reduce the likelihood of erroneous data entry. Data created for analysis will be de-identified and secured on a password protected UNC School of Medicine network hard drive. All investigators will be trained on completing the electronic case report form.

Patient safety will be monitored with continuous cardiovascular monitoring by the critical care team. Subject stopping rules will be in place to end the study intervention, including refractory hypotension, development of pneumothorax, or changes in oxygenation or hemodynamics that the primary team feels may be related to changes in PEEP.

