3.4 Study Population

Inclusion Criteria: Obese adults (BMI ≥ 40) admitted to the MICU at UNC Hospital or the ICU at Vidant Medical Center ECU with acute respiratory failure requiring mechanical ventilation.

Exclusion Criteria:

1. Refusal to give consent by the subject or their LAR
2. Abdominal compartment syndrome
3. Chest tube for pneumothorax
4. Having been on a ventilator for >4 days
5. Suspicion of or known intracranial hypertension
6. Anticipated extubation within 24 hours
7. Chronic ventilator dependence
8. Condition that precludes placement of an esophageal balloon (esophageal or nasopharyngeal pathology preventing insertion of the esophageal balloon catheter, severe thrombocytopenia or coagulopathy)
9. Incarceration
10. Not expected to survive >48 hours
11. Unable to obtain consent from subject or LAR
12. Unable to obtain consent due to a language barrier

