6.2 Statistical Methods

All continuous variables (see 5.2) will be described using mean and standard deviation, with associated 95% confidence intervals, or median with interquartile range as appropriate based on normality of distribution. All categorical variables will be described with frequency and percentage.

To determine if the optimal PEEP has an effect on the duration of mechanical ventilation compared to usual PEEP, the primary outcome will be analyzed with a 2-sided independent t-test. As secondary analysis, the associations between the primary outcome and exposures and demographic variables will be further analyzed using linear regression models.

The impact of optimal PEEP vs standardized PEEP titration will be assessed on all other variables with independent t-tests or chi-square tests as appropriate. All secondary outcomes, as described in 5.2, will be further analyzed with either linear regression models or logistic models, using demographic and exposure variables as predictors.

All tests will be 2-sided, and p-values < 0.05 will be considered significant. Tests with p-values above 0.05 will be considered inconclusive. Missing values will be ignored.

No interim analyses for efficacy or futility are planned, but interim analyses will be conducted for safety.

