6.3 Sample Size and Power

We utilized preliminary data from earlier studies of mechanical ventilation in the obese to establish a baseline. With a mean duration of mechanical ventilation of 7 days with a standard deviation of 2.9 days, we expect the control group to have 21 ventilator free days. We estimate that we could reasonably see an effect in the intervention group that reduces the duration of mechanical ventilation by 3 days. With a power of 80% and alpha=0.05, we would need 16 patients per group, for a total of 32 patients. Would the effect be only a reduction of mechanical ventilation by 2 days, we would need 34 patients in each group for a total of 68 patients. Because the population in our study would be expected to have a lower mean duration of mechanical

ventilation, we anticipate we may find a smaller effect size. Including a possible 10% dropout, we will target a sample size of 76 (38 per group) to safely achieve our goals.

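### Two hospitals enrol, but no stratification by site is stated and the primary t-test has no site term; the test stays valid, but precision is forgone if ventilator-free days differ by site

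*Combined protocol and SAP*

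**What the plan says.** Section 3.4 takes patients "admitted to the MICU at UNC Hospital or the ICU at Vidant Medical Center ECU". Allocation is described twice. Section 3.2 has "Patients will be randomized 1:1 in blocks of 2, 4, or 6", and section 4.2 has "Patients will be randomized 1:1 in random blocks of 2, 4, or 6 to optimal PEEP vs standard PEEP management". Both refer to the REDCap module, and neither names a stratification factor.

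Section 6.2 sets the primary test: "the primary outcome will be analyzed with a 2-sided independent t-test". The same section then plans further regressions of a secondary kind, in which "the associations between the primary outcome and exposures and demographic variables will be further analyzed using linear regression models". The Statistical and Analytic Plan in the synopsis adds a "linear regression model adjusting for BMI, abdominal girth, and Ptp". Site appears in none of these and is not in the variable table in 5.2. The sample size in 6.3 makes no allowance for it.

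On weaning, section 5.1 says of the PEEP threshold at which control patients undergo a spontaneous breathing trial (SBT): "This is the current standard of care based on the SBT protocol at UNC Hospitals". It does not describe the second hospital's usual practice.

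**The concern.** VFD depends directly on when patients come off the ventilator. Section 5.1 leaves part of that to local judgement. Bedside respiratory therapists judge SBT failure, the primary team may extubate control patients before the criteria are met, and tracheostomy follows unit practice. Treatment is open label. Hospital is therefore a foreseeable prognostic factor, and it is known for every patient before randomisation.

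If mean VFD differs between hospitals, an analysis without site leaves that difference in the residual variance. The standard error is then larger than it need be, in a trial sized at 80% power for a 2-day effect.

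**Working it through.** **Inputs from section 6.3.** SD 2.9 days; effect 2 days (3 days in the first scenario); two-sided alpha 0.05; power 80%; 34 evaluable per arm, raised to 38 for 10% dropout.

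**Assumed, because the documents do not give them.** A between-site gap in mean VFD of g = 1, 2 or 3 days, and a site share q of 50:50, 75:25 or 90:10.

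**Step 1: reproduce the plan's figures.** The exact two-sample t-test calculation gives 34 per arm for 2 days (power 80.0%) and 16 per arm for 3 days. Then 34/0.9 = 37.8, so 38 per arm and 76 in total. The plan's numbers reproduce.

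**Step 2: power of the plain t-test if 2.9 is the within-site SD.** The SD that the test sees is sqrt(2.9² + q(1−q)g²). At 34 per arm and a 2-day effect:

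| Split | Gap (days) | SD seen | Power |
|---|---|---|---|
| any | 0 | 2.90 | 80.0% |
| 50:50 | 1 | 2.94 | 78.9% |
| 50:50 | 2 | 3.07 | 75.5% |
| 50:50 | 3 | 3.27 | 70.2% |
| 75:25 | 1 | 2.93 | 79.1% |
| 75:25 | 2 | 3.03 | 76.6% |
| 75:25 | 3 | 3.18 | 72.5% |
| 90:10 | 2 | 2.96 | 78.3% |

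At 50:50 the t-test would need 35, 38 or 43 evaluable per arm to regain 80%. If all 38 per arm are evaluable, power is 84.3% with no gap and 80.1% at a 2-day gap (50:50).

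**Step 3: power if 2.9 already includes site variation.** The within-site SD is then sqrt(2.9² − q(1−q)g²). At 50:50 this is 2.86, 2.72 or 2.48 for gaps of 1, 2 or 3 days. The t-test keeps 80%. A site-adjusted analysis would reach about 81%, 85% or 91%, so the forgone gain is about 1, 5 or 11 points.

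**Step 4: a wider VFD SD.** With an SD of 8, a 2-day gap at 50:50 gives sqrt(64 + 1) = 8.06. At 38 per arm, power moves only from 18.9% to 18.7%.

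**Step 5: chance imbalance is the same effect.** At 34 per arm and 50:50, the between-arm difference in site share has SD sqrt(0.25 × 2/34) = 0.121. With a 2-day gap it contributes 0.121 × 2 = 0.243 day to the standard error. Without site, the standard error is 2.9 × sqrt(2/34) = 0.703. Together, sqrt(0.703² + 0.243²) = 0.744, which equals 3.07 × sqrt(2/34). The imbalance is thus already in the t-test's standard error and is the source of the loss in Step 2.

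**Step 6: simulation (6,000 runs per setting, random blocks of 2, 4 and 6, within-site SD 2.9).**
- Unstratified list, plain t-test: mean estimate on target; type I error 4.6% to 5.3%.
- Unstratified list, site term: power about 79% to 80% at every gap.
- Stratified list, site term: power about 79% to 81%.
- Stratified list, plain t-test, 50:50: type I error 3.7% and 2.7% at gaps of 2 and 3 days, with power about 77% and 72%.

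**The case against.** **No site difference is shown.** The SBT threshold comes from one hospital's protocol but applies to every control patient. Section 5.1 also sets common SBT criteria, failure criteria and tracheostomy-collar steps, all of which narrow site variation. This stands: the gap is an assumption. Local discretion over early extubation and tracheostomy makes a gap plausible but does not establish one.

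**The split may be lopsided.** Section 3.3 projects accrual from a single unit, so 50:50 may overstate the effect. This stands, and the 90:10 row shows how much smaller it becomes.

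**The SD may already be a total SD.** Section 6.3 does not say whether 2.9 is within-site. This stands, and it turns a power loss into a forgone gain. VFD also counts deaths, so its SD may exceed that of ventilation duration, which shrinks the effect further.

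**Site-specific lists have a price.** Treatment is open label and blocks can be as small as 2. Staff at one hospital could follow their own complete sequence and guess the next allocation more easily than from a list interleaved across two hospitals. This stands, and it is why the model term comes first and stratification second.

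**Stronger readings.** A reader might infer that allocation certainly runs from one unstratified list. The sections give block sizes and the REDCap module and are silent on strata. A reader might also infer that chance site imbalance biases the result, or is a harm on top of lost power. Steps 5 and 6 show that it is neither.

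**Conclusion.** The point holds as a matter of efficiency, not validity. Site is missing from the stated allocation and from every stated analysis. The planned t-test remains unbiased on average with its type I error intact.

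On the plan's SD of 2.9, taken as within-site, with 34 evaluable per arm, the cost is negligible at a 1-day gap (about 1 point of power). It is about 2 to 4.5 points at a 2-day gap, depending on the split, and about 10 points at a 3-day gap with equal sites. If 2.9 is a total SD, the planned 80% is untouched and only the gain in Step 3 is missed. Full retention of 38 per arm also absorbs a 2-day gap.

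A reader might conclude that the trial is underpowered because of site. The documents do not support that, since they give no site gap, no split and no statement of what the SD contains. The case for change rests on its very low cost.

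**What to change.** 1. In 6.2, make the primary analysis a linear model for VFD with arm and a fixed effect for site. Add site to the variable table in 5.2, and bring the synopsis into line. The cost is one degree of freedom, 65 instead of 66 with 68 evaluable patients.
2. If randomisation has not begun, also stratify the REDCap list by site and say so in 3.2 and 4.2. The downsides are a possible incomplete block at each site and a more guessable local sequence, so reconsider blocks of 2.
3. If the list is stratified, or already is, keep the site term. A plain t-test after stratification is conservative and leaves most of the power loss in place.
4. If randomisation is under way, leave the list alone and make only the first change. In the simulations, the site term by itself recovered nearly all the power.
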